9.7.8. Week 9 through Week 48 (Safety Contact)

Patients should be contacted by telephone/email at Week 9 and every 3 weeks afterward to Week 48.

- Contact patient by phone/email.
- Review and record prior concomitant medications.
- Assess and record AEs.
- Review and record any non-study related medical or surgical treatment procedures and any medically relevant HCP or non-HCP related office visits that have occurred since the previous study visit.
- Assess investigational product compliance, perform investigational product accountability.

9.7.9. Week 12, Week 24, Week 36 Procedures

- Verify that the patient has fasted for at least 8 hours.

- Record fasting status in the source and eCRF
- If the patient reports having eaten within 8 hours, document accordingly in the source and eCRF and remind the patient that fasting is required prior to all study visits, but water is permitted.
- Assess and record vital signs and weight (oral temperature, sitting heart rate, respiratory rate, and sitting blood pressure).
- Assess and record AEs.
- Perform a physical examination.
- Review and record any non-study related medical or surgical treatment procedures and any medically relevant HCP or non-HCP related office visits that have occurred since the previous study visit.
- Review and record concomitant medications.
- Perform assessments for calculation of CP Score ([Section 14.1.1](#)).
- Administer Quality of Life and Patient questionnaires (see [Section 13.2.6](#)).
- Assess investigational product compliance, perform investigational product accountability.
- Assess for dose titration, if eligible. (Refer to [Section 7.3](#))
- Dispense investigational product only if there is dose increase or as needed. No new investigational product bottles will be dispensed if there is only change in dosing frequency of the same dose level. Patients are expected to use up each investigational product bottle before a new bottle will be dispensed.
- Perform a urine-based β -hCG pregnancy test in females of childbearing potential.
- Obtain blood samples for
 - Serum chemistry, hematology, and coagulation
 - Markers of inflammation and fibrosis (IL-6, hs-CRP, TNF- α , IgM, IgG, IgA, CK-18-M30, ELF [HA, P3NP, and TIMP 1])
 - Bile Acid/C4/FGF-19
 - Fasting PK assessment
- Perform TE using the Fibroscan® TE device. If the TE cannot be performed on visit day (eg, device/technician unavailability, scheduling issues, TE data is needed to inform cirrhosis assessment, etc.), the procedure may be completed within the visit window (if data is needed for cirrhosis assessment) or as close as possible to the visit.
- Perform an ultrasound for HCC surveillance at **Week 24 ONLY** (if equipment is unavailable, sites should make every attempt to use available community referral sites).

- Serial PK assessment at **Week 12 and 24 ONLY (not done at Week 36 and Week 42)**; the following procedures will be conducted in all patients:
 - 30 minutes prior to dosing: collect predose blood sample
 - Dispense/Administer investigational product from the double-blind bottle (collected from the patient upon arrival for this visit) with 240 mL (8 oz.) of water. Instruct the patient to swallow the tablet whole; s/he must not chew, divide, or crush the tablet.
 - Collect blood samples at: 30 min, 45 min, 1 hour postdose
 - Immediately following 1 hour postdose blood draw, administer meal replacement drink (to be consumed within 5 – 10 minutes)
 - Collect blood samples at: 1.5, 2, 2.5, 3, 4, 5, 6, 7, 8, 9, and 24 hours post dose

Note: Patients should only consume a meal following the 4-hour and 7-hour PK assessment times (see [Figure 3](#)). Patients should not drink any water until at least one hour postdose.

- Schedule the next visit, reiterate dosing instructions, and advise the patient:
 - NOT to take investigational product on the morning of the next visit, and
 - To bring the investigational product bottle(s); s/he will dose at the clinic (if this is in compliance with the established dosing frequency), and
 - To fast overnight (at least 8 hours) prior to the next visit. Fasting is required prior to all study visits, but water is permitted.

9.7.10. Week 18 and Week 30 Procedures

- Verify that the patient has fasted for at least 8 hours.
 - Record fasting status in the source and eCRF.
 - If the patient reports having eaten within 8 hours, document accordingly in the source and eCRF and remind the patient that fasting is required prior to all study visits, but water is permitted.
- Perform a physical examination.
- Review and record any non-study related medical or surgical treatment procedures and any medically relevant HCP or non-HCP related office visits that have occurred since the previous study visit.
- Assess and record vital signs and weight (oral temperature, sitting heart rate, respiratory rate, and sitting blood pressure).
- Assess and record AEs.
- Review and record concomitant medications.
- Perform assessments for calculation of CP Score ([Section 14.1.1](#)).
- Administer Quality of Life and Patient questionnaires (see [Section 13.2.6](#)).

- Assess investigational product compliance, perform investigational product accountability.
- Assess for dose titration, if eligible (refer to [Section 7.3](#)).
- Dispense investigational product only if there is dose increase or as needed. No new investigational product bottles will be dispensed if there is only change in dosing frequency of the same dose level. Patients are expected to use up each investigational product bottle before a new bottle will be dispensed.
- Perform a urine-based β -hCG pregnancy test in females of childbearing potential.
- Obtain blood samples for
 - Serum chemistry, hematology, and coagulation
 - Bile Acid/C4/FGF-19
 - Fasting PK assessment
- Serial PK assessment; the following procedures will be conducted in all patients:
 - 30 minutes prior to dosing: collect predose blood sample
 - Dispense/Administer investigational product from the double-blind bottle (collected from the patient upon arrival for this visit) with 240 mL (8 oz.) of water. Instruct the patient to swallow the tablet whole; s/he must not chew, divide, or crush the tablet.
 - Collect blood samples at: 30 min, 45 min, 1 hour postdose
 - Immediately following 1 hour postdose blood draw, administer meal replacement drink (to be consumed within 5 – 10 minutes)
 - Collect blood samples at: 1.5, 2, 2.5, 3, 4, 5, 6, 7, 8, 9, and 24 hours postdose

Note: Patients should only consume meal following the 4-hour and 7-hour PK assessment times (see [Figure 3](#)). Patients should not drink any water until at least one hour post dose

- Schedule the next visit, reiterate dosing instructions, and advise the patient:
 - NOT to take investigational product on the morning of the next visit, and
 - To bring the investigational product bottle(s); s/he will dose at the clinic (if this is in compliance with the established dosing frequency), and
 - To fast overnight (at least 8 hours) prior to the next visit. Fasting is required prior to all study visits, but water is permitted.

9.7.11. Week 48 Procedures

- Verify that the patient has fasted for at least 8 hours.
 - Record fasting status in the source and eCRF

- If the patient reports having eaten within 8 hours, document accordingly in the source and eCRF and remind the patient that fasting is required prior to all study visits, but water is permitted.
- Perform a physical examination, including smoking and alcohol consumption history, and current habits for both.
- Review and record any non-study related medical or surgical treatment procedures and any medically relevant HCP or non-HCP related office visits that have occurred since the previous study visit.
- Assess and record vital signs and weight (oral temperature, sitting heart rate, respiratory rate, and sitting blood pressure).
- Assess and record AEs.
- Review and record concomitant medications.
- Perform ECG.
- Perform assessments for calculation of CP Score ([Section 14.1.1](#)).
- Administer Quality of Life and Patient questionnaires (see [Section 13.2.6](#)).
- Assess investigational product compliance, perform investigational product accountability.
- Assess for dose titration, if eligible (refer to [Section 7.3](#)).
- Dispense investigational product only if there is dose increase or as needed. No new investigational product bottles will be dispensed if there is only change in dosing frequency of the same dose level. Patients are expected to use up each investigational product bottle before a new bottle will be dispensed.
- Perform urinalysis (dipstick)
- Perform a urine-based β -hCG pregnancy test in females of childbearing potential.
- Obtain blood samples for
 - Serum chemistry, hematology, and coagulation
 - Markers of inflammation and fibrosis (IL-6, hs-CRP, TNF- α , IgM, IgG, IgA, CK-18-M30, ELF [HA, P3NP, and TIMP 1])
 - Fasting PK assessment
 - Bile Acids/C4/FGF-19
- Serial PK assessment; the following procedures will be conducted in all patients:
 - 30 minutes prior to dosing: collect predose blood sample
 - Dispense/Administer investigational product from the double-blind bottle (collected from the patient upon arrival for this visit) with 240 mL (8 oz.) of water.
 - Collect blood samples at: 30 min, 45 min, 1 hour postdose

- Immediately following 1 hour post dose blood draw, administer meal replacement (to be consumed within 5 – 10 minutes)
- Collect blood samples at: 1.5, 2, 2.5, 3, 4, 5, 6, 7, 8, 9, and 24 hours post dose

Note: Patients should only consume meal following the 4-hour and 7-hour PK assessment times (see [Figure 3](#)). Patients should not drink any water until at least one hour post dose

- Perform TE using the Fibroscan® TE device. If the TE cannot be performed on visit day (eg, device/technician unavailability, scheduling issues, TE data is needed to inform cirrhosis assessment, etc.), the procedure may be completed within the visit window (if data are needed for cirrhosis assessment) or as close as possible to the visit.
- Perform an ultrasound for HCC surveillance (if equipment is unavailable, sites should make every attempt to use available community referral sites).
- Schedule the next visit, reiterate dosing instructions, and advise the patient:
 - NOT to take investigational product on the morning of the next visit, and
 - To bring the investigational product bottle(s); s/he will dose at the clinic (if this is in compliance with the established dosing frequency), and
 - To fast overnight (at least 8 hours) prior to the next visit. Fasting is required prior to all study visits, but water is permitted.

9.7.12. Every 3 Months after Week 48

Quarterly

- Verify that the patient has fasted for at least 8 hours.
 - Record fasting status in the source and eCRF
 - If the patient reports having eaten within 8 hours, document accordingly in the source and eCRF and remind the patient that fasting is required prior to all study visits, but water is permitted.
- Perform a physical examination, including smoking and alcohol consumption history, and current habits for both.
- Review and record any non-study related medical or surgical treatment procedures and any medically relevant HCP or non-HCP related office visits that have occurred since the previous study visit.
- Assess and record vital signs and weight (oral temperature, sitting heart rate, respiratory rate, and sitting blood pressure).
- Assess and record AEs.
- Review and record concomitant medications.
- Perform assessments for calculation of CP Score ([Section 14.1.1](#)).

- Administer Quality of Life and Patient questionnaires (see [Section 13.2.6](#)).
- Assess investigational product compliance, perform investigational product accountability.
- Assess for dose titration, if eligible (refer to [Section 7.3](#)).
- Dispense investigational product only if there is dose increase or as needed. No new investigational product bottles will be dispensed if there is only change in dosing frequency of the same dose level. Patients are expected to use up each investigational product bottle before a new bottle will be dispensed.
- Perform a urine-based β -hCG pregnancy test in females of childbearing potential.
- Obtain blood samples for
 - Serum chemistry, hematology, and coagulation
- Schedule the next visit, reiterate dosing instructions, and advise the patient:
 - NOT to take investigational product on the morning of the next visit, and
 - To bring the investigational product bottle(s); s/he will dose at the clinic (if this is in compliance with the established dosing frequency), and
 - To fast overnight (at least 8 hours) prior to the next visit. Fasting is required prior to all study visits, but water is permitted.

Patients will complete a TE/ELF (HA, P3NP and TIMP 1) and ultrasound (for HCC surveillance) assessment, every 6 months (± 2 weeks) after Week 48.

ECG and urine will be done yearly (± 2 weeks) after Week 48.

9.7.13. End of Study/Early Termination/End of Treatment Procedures for Patients that Withdraw from Investigational Product or Withdraw Consent

Patients who discontinue investigational product before Week 48 are expected to continue in the study until the end of the study (EOS [when subject terminates the study]) or at the discretion of the Sponsor.

EOT (when subject discontinues investigational product)/ET procedures will be required whenever patients discontinue treatment with investigational product ([Table 1](#), [Section 9.7.11](#)). The EOT/ET Visit ([Table 1](#)) and procedures listed below ([Table 4](#)) must be performed as close as possible to the patient's last dose of investigational product. When a patient discontinues or interrupts investigational product and continues with regularly scheduled study visits, the EOS Visit will be completed as the patient's final study visit. The actual investigational product discontinuation scenario ([Table 4](#)) will determine the sequence of the EOT/ET and EOS Visits and procedures. In some cases, the EOT/ET Visit and procedures will precede the EOS Visit; in others, the EOT/ET and EOS Visits will be combined and performed as close as possible to the patient's last dose of investigational product. EOT and EOS Visits are encouraged but at no time will a missed EOT or EOS visit be considered a protocol deviation.

When a patient ends her/his participation in the study (eg, at a point between standard study visits) either due to early termination (ET) (withdrawal of consent) or discontinuation, an

EOT/EOS Visit must be performed as near as possible to her/his last dose of investigational product and the procedures, listed below, performed. The purpose of this visit is to conduct complete and/or final assessments on or as near as possible to the final day of dosing. In some cases, the patient may discontinue on the day of a scheduled study visit. In these cases, EOT/EOS Visit procedures should be performed in place of the scheduled study visit procedures. The data will be recorded as EOT/ET and EOS procedures in the eCRF.

Table 4: Early Discontinuation Scenarios

	Investigational Product	Consent	Study Visit Status	EOT Visit ^a	EOS Visit ^a
Early Termination	Discontinued	Withdrawn	No additional visits except EOT/EOS	Combined visit, completed as close as possible to last dose of investigational product.	
Treatment Discontinuation^b	Discontinued	Active	Regular Visit Schedule	Complete as close as possible to last dose of investigational product.	Complete at final study visit.
	Discontinued	Record review only	Record review only	Combined visit, completed as close as possible to last dose of investigational product.	
Sponsor Termination	Discontinued	N/A	No additional visits except EOT/EOS	Combined visit, completed as close as possible to last dose of investigational product.	
Pregnancy	Discontinued	Complete per the above scenarios - Early Termination or Treatment Discontinuation			
Lost to Follow-Up	Discontinued	LTF	None	Unable to complete due to LTF status	

EOS = end of study; EOT = end of treatment; LTF = lost to follow-up

^a Refer to [Section 7.1.2](#), Schedule of Study Procedures for all procedures and evaluations required at the EOS and EOT Visits.

^b Includes initiation of commercially available OCA.

9.7.14. Unscheduled Safety Visit

The Investigator may schedule an at-clinic Unscheduled/Safety Visit at any time if clinically warranted. Unscheduled and/or repeat assessments, including additional laboratory tests or investigations, may be conducted.

As appropriate, the Medical Monitor should be contacted.

10. INVESTIGATIONAL PRODUCT MATERIALS AND MANAGEMENT

10.1. Investigational Product

The investigational product is a white, round, film coated tablet containing OCA 5 mg or 10 mg or matching placebo. The tablets contain the following inactive ingredients: microcrystalline cellulose, sodium starch glycolate, and magnesium stearate.

10.2. Investigational Product Packaging and Labeling

The packaging and labeling of investigational product supplies will be performed according to Good Manufacturing Practice standards by a designated qualified vendor. All investigational product will be provided as tablets for oral administration and provided in high density polyethylene bottles with heat induction seals and child resistant closures. The bottle packaging will not reveal any information about the treatment dose contained in the bottle. Multiple bottles may be dispensed to the patient at each visit to provide enough tablets for dosing until the next visit.

The designated investigational product packaging/distribution vendor will also be responsible for the distribution of the investigational product to the Investigator.

10.3. Investigational Product Storage

All OCA tablet strengths provided to clinical study sites in support of clinical studies are to be shipped and stored at 15°C to 25°C. Temperature excursions within the range of 2°C and 30°C for no more than a 6-month period are acceptable, and the OCA tablet continues to be suitable for use in clinical studies. Additionally, temperature excursions within the range -20°C to 40°C for no more than 7 days are acceptable, and the OCA tablet continues to be suitable for use in clinical studies.

10.4. Investigational Product Administration

Refer to [Section 9.1](#).

10.5. Investigational Product Accountability and Disposal

The Sponsor's representative will send investigational product to the study site under appropriate storage conditions. All shipments of investigational product should be unpacked and the contents reviewed immediately upon receipt. If it is not possible to verify the contents immediately, they must be stored under the appropriate storage conditions until verification of the contents is possible (ideally, within 1 business day from receipt). The pharmacist or designee should verify the investigational product against the shipment documentation. The pharmacist or designee should contact the Sponsor immediately to report any concerns regarding the shipment.

All investigational product will be provided for use only in this study and is not to be used for any other purpose. The Investigator or designee will maintain a full record of investigational product accountability, including records of individual patient dispensing and final return or disposition (as directed by the Sponsor).

The study monitor, also known as the Clinical Research Associate (CRA), will review accountability records against investigational product dispensed and that remaining in stock, during on site monitoring visits and when the study is completed, or if it is prematurely terminated. The CRA will retrieve documentation detailing and confirming the return or destruction of the investigational product. If the investigational product is to be returned to the Sponsor's vendor for destruction, the CRA will also prepare the investigational product for shipment.

11. OVERVIEW OF ASSESSMENTS

The assessments supporting the objectives for the study are in Table 5:

Table 5: Table of Assessments

Primary Objectives	Assessments
PK parameters	OCA and its conjugates glyco-OCA and tauro-OCA, and metabolite OCA glucuronide
Safety and tolerability	SAEs and TEAEs, physical exam, ECG, vital signs, clinical laboratory assessments, discontinuations, pruritus, and fatigue
Secondary Objectives	Assessments
Changes in risk scores	Changes in MELD and CP Score components
Changes in liver biochemistry and hepatobiliary damage	Total and direct bilirubin, ALP, ALT, AST, GGT, INR, creatinine, albumin, platelets
PD parameters	FGF-19, C4, and plasma bile acids
Additional Objectives	Assessments
Markers of inflammation	IL-6, hs-CRP, TNF- α , IgM, IgA, IgG, CK-18-M30,
Noninvasive measurements of liver fibrosis, liver stiffness and cirrhosis	Transient Elastography/ELF (HA, P3NP, and TIMP-1)
PK/PD relationship	PK parameters compared to PD Parameters and Safety and Tolerability assessments (above)
Patient-reported outcomes	Pruritus VAS, PBC-40, EQ-5D-5L, CLDQ
Clinical events	Death (all-cause and liver-related), liver transplant, Model of end stage liver disease (MELD) score ≥ 15 (for patients with MELD ≤ 12 at baseline), Hospitalization for new onset or recurrence of: variceal bleed, hepatic encephalopathy, spontaneous bacterial peritonitis, Uncontrolled ascites, and HCC.

ALP = alkaline phosphatase; ALT = alanine aminotransferase; AST = aspartate aminotransferase; C4 = 7 α -hydroxy-4-cholesten-3-one; CK-18-M30 = cytokeratin-18 neopeptide-M30; CLDQ = Chronic Liver Disease Questionnaire; CP = Child-Pugh; ECG = electrocardiogram; ELF = enhanced liver fibrosis; FGF-19 = fibroblast growth factor-19; GGT = gamma-glutamyl transferase; HA = hyaluronic acid; hs-CRP = high-sensitivity C-reactive protein; IgA = immunoglobulin A; IgG = immunoglobulin G; IgM = immunoglobulin M; IL-6 = interleukin 6; INR = international normalized ratio; MELD = Model End Stage Liver Disease; OCA = obeticholic acid; P3NP = procollagen 3 N-terminal peptide; PBC = Primary Biliary Cholangitis; PD = pharmacodynamic; PK = pharmacokinetic; SAE = serious adverse event; TE = Transient Elastography; TEAE = treatment emergent adverse events; TIMP-1 = tissue inhibitor of metalloproteinase 1; TNF- α = tumor necrosis factor; VAS = visual analog scale

12. CLINICAL PHARMACOKINETIC ASSESSMENTS

Pharmacokinetic analyses will be based on the PK population ([Section 15.1](#)). Patients in the PK Population with at least one PD assessment after dosing will be included in the combined PK/PD analyses.

[figure not shown]

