6.3. Additional Objectives

- To evaluate the effect of OCA treatment compared to placebo on:
 - Markers of inflammation
 - Noninvasive markers of liver fibrosis (Enhanced Liver Fibrosis [ELF]TM score)
 - Noninvasive measurement of liver stiffness (transient elastography [TE])
- To assess the PK/Pharmacodynamic (PD) relationship of OCA with:
 - PK parameters compared to PD Parameters and Safety and Tolerability assessments
- To assess patient reported outcomes (Pruritus Visual Analogue Scale [VAS], PBC-40, EQ 5D-5L, Chronic Liver Disease Questionnaire [CLDQ])
- To assess clinical events consistent with end-stage liver disease
 - Death (all-cause)
 - Liver transplant
 - Model of end stage liver disease (MELD) score ≥ 15 (for patients with MELD ≥ 12 at baseline)
 - Hospitalization (as defined by a stay of 24 hours or greater) for new onset or recurrence of: variceal bleed, hepatic encephalopathy (as defined by a West Haven score of ≥ 2), spontaneous bacterial peritonitis
 - Uncontrolled ascites (diuretic resistant ascites requiring therapeutic paracentesis at a frequency of at least twice in a month)
 - Hepatocellular carcinoma (HCC)

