7.3. Planned Dosing Regimen

All patients will initiate investigational product once weekly with OCA 5 mg or matching placebo (Table 2). Titration may be considered as early as the Week 12 Visit. Following visit procedures at Week 12, if the investigational product is tolerated and laboratory assessments do not indicate a safety concern, the patient may up-titrate to OCA 5 mg twice weekly and may start the higher dose regimen no earlier than 2 days after they took their last dose. Dosing will then occur at least 3 days apart. Every 6 weeks thereafter, based on safety and tolerability assessments, patients can be considered for further up titration as described below (Table 2). At each titration visit, the patient may start the higher dose regimen no earlier than 2 days after the prior dose.

Patients with CP-B may titrate to a maximum dose of OCA 5 mg once daily.

Patients with CP-C may titrate to a maximum dose of OCA 10 mg twice weekly at least 3 days apart.

If, during the course of the study, a patient transitions from CP- B to CP-C, or vice versa, the maximal dose for the new CP classification would apply (Table 3).

Table 2: Planned OCA or Matching Placebo Dosing Regimen by Child-Pugh Score

	Child-Pugh B (Moderate Hepatic Impairment)		Child-Pugh C (Severe Hepatic Impairment)	
	Treatment Group		Treatment Group	
	OCA	Placebo	OCA	Placebo
Starting Dose (Day 1)	5 mg once weekly	matching placebo	5 mg once weekly	matching placebo
Titration 1^a	5 mg twice weekly ^b	matching placebo	5 mg twice weekly ^b	matching placebo
Titration 2^a	10 mg twice weekly ^b	matching placebo	10 mg twice weekly ^b	matching placebo
Titration 3^a	5 mg once daily	matching placebo	NA	NA

^a Planned titration regimen is shown; however, the titration of dose and/or frequency is dependent on patient tolerability and/or changes in Child-Pugh Score at any time during the study.

^b Dosing per the twice weekly schedule must be at least 3 days apart.

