7.4. Dose Adjustment Criteria

Dose titration may follow the scheduled dosing regimens described in [Section 7.3](#) or occur due to tolerability concerns or as a result of changes in a patient's CP Score.

Dose titrations may involve increases or decreases in dosing frequency and are dependent on tolerability (as assessed by a review of AEs and safety laboratory results). In general, down-titration may be done in response to tolerability concerns and can occur at any time. Up-titration will be done per protocol based on tolerability, as assessed by the Investigator based on response, or following resolution of a tolerability concern that previously led to down-titration. Up-titrations may only occur to the maximum dose and frequency indicated for each dosing regimen as defined in [Section 7.3](#).

Scheduled Dose Titration - After initiation of OCA or matching placebo, titration may be considered as early as the Week 12 Visit. Subsequent titrations in dose or dosing frequency for patients may occur no earlier than 6 weeks following an up-titration.

Tolerability Dose Titration - Investigators may decrease the dosing frequency or dose as considered clinically appropriate (eg, tolerability)

Dose Titration due to Change in CP Score – Over the course of the study, a patient's CP category may change. When a patient demonstrates a change in CP category (as assessed per [Table 10](#)), dosing should be reassessed and modified if appropriate ([Table 2](#)). Changes to the dosing regimen are not mandatory and should be based on clinical judgment and change in CP score. The titration steps for CP-B and CP-C patients are identical with exception of the maximum allowed dose. Therefore, if a patient changes CP class from B to C, or vice versa, the maximal dose for the new regimen will apply ([Table 3](#)). If a patient improves to CP-A during the study, the maximal CP-B dose will still apply. If a patient has not yet reached the maximal dose, the appropriate titration regimen ([Table 2](#)) should be followed.

Table 3: Maximum Daily dose based on change in Child-Pugh Category

Original Status	New Status ^a		
	Child-Pugh A	Child-Pugh B	Child-Pugh C
Child-Pugh B	No change	No change	10 mg twice weekly
Child-Pugh C	5 mg once daily	5 mg once daily	No change

^a Once a patient begins dosing with the new dosing regimen, titration should occur as described for that dosing regimen in [Section 7.3](#).

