14.2.3. Markers of FXR activation

Blood samples will be collected in all patients to measure C4, FGF-19, and bile acids. The results of these analyses will be used to assess the PK/PD response of OCA. Blood samples will be assessed in patients according to the schedule presented in see [Table 1](#).

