15.1. Analysis Populations

The following patient populations will be evaluated and used for presentation and analysis of the data:

- The Intent-to-Treat (ITT) Population will include all randomized patients who receive any amount of investigational product (OCA or placebo). The ITT Population will be the primary population used for summarizing efficacy assessments.
- The Safety Population will include all patients who received at least one dose of investigational product (placebo or OCA). The Safety Population will be the primary population used for safety analyses.
- The PK population will include all patients receiving OCA who have adequate concentration-time profiles to characterize OCA and its conjugates and must not have any major protocol deviations that potentially affect exposure levels.

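### The PK/PD analysis set leaves out every placebo patient, although their PD and safety data are collected; including them at zero exposure with a time term would sharpen the exposure-response estimate at almost no cost

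*Protocol*

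**What the plan says.** All references are to Protocol Version 2.

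- **Analysis set.** Section 12: "Patients in the PK Population with at least one PD assessment after dosing will be included in the combined PK/PD analyses". Section 15.1: "The PK population will include all patients receiving OCA who have adequate concentration-time profiles to characterize OCA and its conjugates". Read together, these admit only OCA recipients to the PK/PD analyses.
- **Objective.** Section 6.3 lists the PK/PD relationship among the additional objectives, as "PK parameters compared to PD Parameters and Safety and Tolerability assessments". It therefore covers safety and tolerability as well as PD markers.
- **Data collected.** Section 14.2.3: "Blood samples will be collected in all patients to measure C4, FGF-19, and bile acids". The same section says these results serve the assessment of the PK/PD response. Table 1 gives both arms one schedule for PD markers, chemistry and adverse events.
- **Titration.** Section 7.3: from Week 12 "the patient may up-titrate to OCA 5 mg twice weekly", and every 6 weeks after that "patients can be considered for further up titration as described below". Section 7.4: "down-titration may be done in response to tolerability concerns and can occur at any time". The ceiling is 5 mg daily for CP-B and 10 mg twice weekly for CP-C.
- **Model.** The protocol states no PK/PD model and does not say whether time is adjusted for.

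**The concern.** Dose starts low and, where it changes as planned, moves up over the same 48 weeks in which liver disease may progress. Section 8.4.1.2 itself treats gradual elevations in liver enzymes or bilirubin as possible disease progression. Among OCA patients, later visits tend to be both higher-exposure and further-progressed visits. A PK/PD regression that ignores time would credit progression to exposure, for instance as an apparent rise in bilirubin with OCA concentration.

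Placebo patients show the course without drug and supply the zero-exposure end of the relationship. The Section 12 rule removes them from this one analysis and sits awkwardly with Section 14.2.3. Section 5.4.1 says the study should help inform benefit-risk in hepatically impaired patients, so a noisy or misattributed exposure-response on liver chemistry or safety would matter.

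**Working it through.** The protocol gives no figure for the PK/PD analysis, so there is none to reproduce. Section 15.2 builds the total as 20 + 10 + 20 = 50. The 1:1 allocation in Section 9.4.1 makes that about 25 OCA and 25 placebo.

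**1. Dose against time.** Weekly totals follow from Table 2: 5 mg weekly = 5, 5 mg twice weekly = 10, 10 mg twice weekly = 20, 5 mg daily = 35. On the fastest permitted path:

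| Week | 6 | 12 | 18 | 24 | 30 | 36 | 48 |
|---|---|---|---|---|---|---|---|
| CP-B, mg/week | 5 | 5 | 10 | 20 | 35 | 35 | 35 |
| CP-C, mg/week | 5 | 5 | 10 | 20 | 20 | 20 | 20 |

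Pearson correlation, r = Sxy / √(Sxx·Syy):
- CP-B: 1135.7 / √(1254.9 × 1221.4) = 0.92.
- CP-C: 544.3 / √(1254.9 × 321.4) = 0.86.
- Serial PK visits only (Weeks 12, 18, 24, 30, 48): 678 / √(763.2 × 770) = 0.88 for CP-B and 300 / √(763.2 × 200) = 0.77 for CP-C.

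**2. What omitting time does.** With no drug effect and linear drift, the within-patient slope without a time term has expectation drift × S(dose, week) / S(dose, dose) / 48 per mg/week. On the CP-B path, with Day 1 entered at zero exposure, this is drift × 1586.25 / 1596.875 / 48 = drift × 0.0207 per mg/week. That is 0.72 × drift per 35 mg/week, or 0.41 × drift per 20 mg/week. The protocol gives no drift. For assumed log-bilirubin drifts of 0.1, 0.2 and 0.3 over 48 weeks, the spurious slope per 20 mg/week is 0.04, 0.08 and 0.12.

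**3. Separating the time term from the placebo patients.** The simulation used a true exposure effect of 0, 25 patients per arm, 20% CP-C, patient fixed effects and 600 runs per row. Drift was 1 residual SD over 48 weeks. The probability of stepping up at each permitted visit was 1.0, 0.6 or 0.3, and the between-patient log-exposure SD was 0.3 or 0.7. The last three are assumptions. Slopes are in residual SDs per 35 mg/week-equivalent.

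| Step-up prob. | Log-SD | Within-patient r (exposure, time) | OCA only, no time: mean slope | OCA only + time: mean (SD) | Placebo added + time: mean (SD) | SD reduction |
|---|---|---|---|---|---|---|
| 1.0 | 0.3 | 0.89 | 0.646 | 0.001 (0.350) | 0.002 (0.202) | 42% |
| 1.0 | 0.7 | 0.75 | 0.395 | 0.007 (0.191) | 0.007 (0.145) | 24% |
| 0.6 | 0.3 | 0.85 | 0.775 | 0.011 (0.405) | 0.001 (0.257) | 37% |
| 0.6 | 0.7 | 0.72 | 0.468 | -0.027 (0.226) | -0.014 (0.184) | 19% |
| 0.3 | 0.3 | 0.73 | 1.111 | 0.006 (0.511) | 0.004 (0.401) | 22% |
| 0.3 | 0.7 | 0.64 | 0.741 | -0.009 (0.378) | -0.003 (0.318) | 16% |

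SD reduction is 1 minus the ratio of SDs; for the first row, 1 - 0.202/0.350 = 0.42.

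- Without time, OCA-only analysis was falsely significant at the nominal 5% level in 79% to 98% of runs. With time, the rate was 4% to 7%.
- Adding placebo without time left the mean slope exactly as in the OCA-only column (0.646 in the first row). Under patient fixed effects a placebo patient's exposure never varies, so that patient adds nothing to the slope unless time is in the model.

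**4. A second set-up.** With log-bilirubin drifts of 0.1, 0.2 and 0.3, residual SD 0.15 and log-exposure SD 0.5, OCA-only slopes without time were 0.041, 0.081 and 0.118. With time they were -0.002, 0.002 and -0.003. With placebo and time they were -0.001, 0.000 and -0.003. The slope SD fell from about 0.027 to 0.022, or 19%.

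**The case against.** The strongest reply is that any bias comes from an assumed model and not from the population rule. Section 12 fixes who is included and nothing in the protocol forbids a time covariate, which is commonly specified in the SAP. Steps 3 and 4 bear this out: the time term removes all of the bias and placebo patients remove none. This stands, and it reduces the point to one of precision.

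Three stronger readings are tempting, and the documents do not support them.
- *Titration is forced.* Sections 7.3 and 7.4 make it optional, dependent on tolerability and reversible, with different ceilings for CP-B and CP-C.
- *Exposure and time are almost the same variable.* The 0.92 is weekly dose on the fastest CP-B path. With optional titration and exposure spread, the simulated within-patient correlation is 0.64 to 0.89. The tablet strength taken at CP-B serial visits (5, 5, 10, 5, 5 mg) correlates with week at only -0.10, so per-dose parameters may be less affected.
- *Drift and exposure cannot be separated within OCA patients.* They can, with a time term, though less precisely.

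It is also fair to say that placebo comparison exists elsewhere. Section 15.5 compares liver chemistry, CP and MELD changes between arms, and Section 15.4 summarises safety by arm. A drift shared by both arms would be visible there. That does not make the PK/PD estimate itself more precise.

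What the reply leaves standing is that Section 12 is a stated rule, not an omitted detail, and an SAP that follows it inherits the exclusion.

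**Conclusion.** The point holds as a cheap improvement. Sections 12 and 15.1 exclude about 25 of 50 patients from the PK/PD analyses, although the data needed from them are already collected. Exposure is strongly correlated with time on the planned titration, so disease drift can be read as an exposure effect if time is not modelled. With time modelled, OCA-only analysis is unbiased in simulation, and adding placebo at zero exposure lowers the slope SD by 16% to 42%.

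Those percentages rest on the assumed step-up probability and exposure spread, on linear drift common to both arms, and on titration unrelated to outcome. The last assumption matters. Under Sections 7.3 and 7.4, patients who tolerate treatment are the ones titrated up, and neither placebo data nor a time term removes that confounding, which could act in either direction. Because this is an additional objective and Section 15 plans no formal hypothesis testing, the consequence is moderate.

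**What to change.** 1. In Section 12, define the PK/PD set as the PK Population plus dosed placebo patients with at least one post-dose PD or safety assessment, with placebo exposure set to zero. Section 8.4.3 expects patients who start commercial OCA to stay in the study, so state how placebo records after that point are handled, since zero exposure no longer applies to them.
2. State that the model includes time since first dose and baseline CP class. Item 1 without the time term gains nothing.
3. Keep the OCA-only analysis, with the same time term, as a sensitivity analysis.
4. Align Section 12 with Section 14.2.3 on whose PD results enter the PK/PD assessment.
5. State as a limitation that confounding of titration by tolerability remains.

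The cost is a short edit to Section 12 and slightly more modelling work. No new samples, visits or patients are needed.
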